- d As of Week 64, patients receiving ixekizumab 80 mg Q4W during Period 3 may have their dose escalated to ixekizumab 80 mg Q2W if the investigator determines that the patient may benefit from an increase in frequency of dosing to achieve adequate disease control. However, for patients in Group B, escalation to ixekizumab 80 mg Q2W may occur only after the patient has been retreated upon flare with the ixekizumab treatment regimen received during Period 1 (ixekizumab 80 mg Q4W) for at least 12 weeks.
- e For patients who were receiving ixekizumab in the originating study, the dose in the 24-week Lead-In Period (Period 1) will be based on the current dosing in the originating study. For patients in Study RHBX who were on placebo, patients will receive ixekizumab 80 mg Q4W.

Figure RHY.1. Illustration of study design for Clinical Protocol I1F-MC-RHY.

Lead-In Period (Period 1): Patients who were previously receiving ixekizumab treatment during Studies RHBV and RHBW will, as of Week 0 in Study RHY, continue to receive the same ixekizumab treatment regimen they were on at the end of the originating study, but now in open-label fashion.

For patients in Study RHBX, treatment during the Lead-In Period will be assigned as follows:

- Patients who were rescued to ixekizumab 80 mg Q2W will remain on ixekizumab 80 mg Q2W in open-label fashion.
- Patients who were receiving blinded treatment with either ixekizumab 80 mg Q2W or ixekizumab 80 mg Q4W will continue on their ixekizumab dose regimen in blinded fashion.
- Patients who were receiving blinded treatment with placebo will be assigned to receive blinded treatment with ixekizumab 80 mg Q4W.

Note: Patients from Study RHBX on blinded therapy in Period 1 of Study RHY will continue on blinded treatment until at least the Week 52 datalock has occurred for Study RHBX.

Patients, site personnel, and the Sponsor will remain blinded to the initial treatment patients were assigned to in Studies RHBV, RHBW, and RHBX until after completion of datalock for the respective originating study (i.e., Week 16 datalock for Studies RHBV and RHBW, and Week 52 datalock for Study RHBX).

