7.3. Blinding

Patients, study site personnel, and study team in Study RHBY will remain blinded to the initial treatment assigned in the originating study (RHBV, RHBW, or RHBX) until the time of datalock for the respective originating study (i.e., Week 16 datalock for Studies RHBV and RHBW, and Week 52 datalock for Study RHBX).

During the Lead-In Period (Period 1), all patients from studies RHBV and RHBW will receive treatment with either ixekizumab 80 mg Q2W or ixekizumab 80 mg Q4W in open-label fashion. For patients from Study RHBX, patients who were rescued to open-label treatment with

ixekizumab 80 mg Q2W will continue to receive open-label treatment with ixekizumab 80 mg Q2W during the Lead-In Period. All other patients from Study RHBX will continue on blinded treatment in the extension Study RHBY until Week 52 datalock has occurred for Study RHBX.

During the Extension Period (Period 2), including blinded, randomized withdrawal-retreatment, patients who do not meet entry criteria for participation in the randomized withdrawal-retreatment period (Group A) will continue to receive ixekizumab 80 mg Q2W or ixekizumab 80 mg Q4W. Patients having achieved a state of sustained remission and do meet the criteria outlined in Section 5.1 (Group B) will participate in the double-blind, placebo-controlled, randomized withdrawal-retreatment period. During the randomized withdrawal-retreatment period, patients in Group B, study site personnel, and study team will be blinded to study treatment randomization. Patients participating in the randomized withdrawal-retreatment period will continue to receive blinded treatment until the completion of the study or time of flare. Upon flare, patients will be retreated with the ixekizumab treatment regimen assigned in Period 1 in an open-label fashion. Patients who experience a flare and were originally from Study RHBX will not receive open-label treatment until the Week 52 datalock has occurred for Study RHBX.

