10.2. Populations for Analyses

For purposes of analysis, the following major patient populations are defined ([Table RHBY.5](#)).

Table RHBY.5. Major Patient Populations for Study RHBY

Population	Description
Lead-In Period Safety Population	All patients who receive at least 1 dose of ixekizumab in Period 1.
Randomized Withdrawal Intent-to-Treat (ITT) Population	All patients who are randomized in Period 2 (Group B), even if the patient does not receive the correct treatment or does not follow the protocol. Patients will be analyzed according to the treatment which they were assigned.
Randomized Withdrawal Safety Population	All patients in Group B who receive at least 1 dose of study treatment after Period 2 randomization. Patients will be analyzed according to the treatment to which they were assigned.
Ixekizumab Structure Population	All patients who (i) are from either RHBV or RHBW study; (ii) have been treated with ixekizumab for at least 18 months; and (iii) have mSASSS data at both Week 0 in the originating study and Week 56 in RHBY.
Long-Term Ixekizumab Treatment Efficacy Population	All patients who are randomized to ixekizumab 80 mg Q2W or ixekizumab 80 mg Q4W at Week 0 of the originating studies and consistently received ixekizumab in RHBY.
Flare Population	All patients in Group B who experience a flare after randomization at Week 24 and who receive ixekizumab retreatment after flare in Period 2 and Periods 2 and 3 combined (exploratory analyses).
Follow-Up Period Population	All patients who receive at least 1 dose of study treatment at any time during Study RHBY and enter the Post-Treatment Follow-Up Period (Period 4). Patients will be analyzed according to the treatment they were taking before entering Period 4.

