### **6.1.1. Analysis Populations**

The following analysis populations will be used to address the study objectives.

**Lead-In Period Safety Population:** Unless otherwise specified, safety summaries for Combined Periods 1, 2, and 3 will be conducted on the Lead-In Period Safety Population, defined as all patients who receive at least 1 dose of ixekizumab in Period 1 in RHBY. Patients who do not meet entry criteria for participation in the randomized withdrawal-retreatment period (Group A) will continue to receive ixekizumab 80 mg Q2W or ixekizumab 80 mg Q4W. Patients who meet the entry criteria (Group B) may be randomized to ixekizumab or placebo at Week 24. Patients randomized to placebo may be retreated upon flare with the ixekizumab regimen that they received in Period 1. The data while on placebo is not included in the combined period analysis. For immunogenicity data analysis during the combined periods 1, 2, and 3, all data will be included regardless of being re-randomized to placebo or ixekizumab. Patients will be analyzed according to the treatment they were receiving at the start of Period 1.

**Long-Term Ixekizumab Treatment Efficacy Population:** Unless otherwise specified, efficacy and health outcome for Combined Periods 1, 2, and 3 will be summarized for the Long-Term Ixekizumab Treatment Efficacy Population, defined as patients who are randomized to ixekizumab 80 mg Q2W or ixekizumab 80 mg Q4W at Week 0 of the originating studies and consistently receive the same treatment regimen through Week 64 in RHBY. Patients who were randomized to placebo or adalimumab in any of the originating studies, patients who switched from IXEQ4W to open label to IXEQ2W during the originating study of RHBY, patients who were randomized to placebo during Period 2 of RHBY, and patients who were retreated during Period 2 of RHBY are not included in this population. Patients will be analyzed according to the ixekizumab regimen they were randomized to at Week 0 of the originating study.

**Ixekizumab Structure Population:** The analysis of 2-year radiographic progression in spine, measured by the change in mSASSS in patients with active rad-axSpA, will be conducted on Ixekizumab Structure Population, defined as all patients who i) are from either RHBV or RHBW study; and ii) have mSASSS data at both Week 0 in the originating study and Week 56 in RHBY.

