**Treatment Groups and Major Patient Populations for Analysis Periods for Study RHBY**

Abbreviations: ITT = intent-to-treat; IXE = ixekizumab; IXE-Structure = patients from Ixekizumab Structure Population; IXE80Q2W = ixekizumab 80 mg every 2 weeks; IXE80Q4W = ixekizumab 80 mg every 4 weeks; PBO = placebo; RW = randomized withdrawal; Total IXE = IXE80Q2W and IXE80Q4W combined in RHBY; vs. = versus.

- a IXEQ2W is a group of patients who have been treated consistently with ixekizumab 80 mg every 2 weeks since Week 0 in the originating studies through Week 64 of RHBY. IXEQ4W is a group of patients who have been treated consistently with ixekizumab 80 mg every 4 weeks since Week 0 in the originating studies through Week 64 of RHBY.

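### The long-term efficacy population handles originating-study rescue differently by dose: a rescued Q4W patient is excluded, a rescued Q2W patient would stay

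*SAP*

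**What the plan says.** SAP 6.1.1 admits patients randomized to either ixekizumab regimen at Week 0 of the originating study who "consistently receive the same treatment regimen through Week 64 in RHBY". It then names several exclusions. One is dose-specific: "patients who switched from IXEQ4W to open label to IXEQ2W during the originating study of RHBY". Another applies to both doses: "patients who were retreated during Period 2 of RHBY are not included in this population". Columns are formed by original assignment: "Patients will be analyzed according to the ixekizumab regimen they were randomized to at Week 0 of the originating study". The footnote to Table RHBY.6.1, repeated under Tables RHBY.6.5 and RHBY.6.7, describes the Q2W column in terms of regimen only: "IXEQ2W is a group of patients who have been treated consistently with ixekizumab 80 mg every 2 weeks since Week 0". Table RHBY.6.1 marks this population as descriptive.

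Protocol 10.2 (Table RHBY.5) defines the same population more widely, as patients "randomized to ixekizumab 80 mg Q2W or ixekizumab 80 mg Q4W at Week 0 of the originating studies and consistently received ixekizumab in RHBY". It does not require an unchanged regimen and does not exclude Q4W-to-Q2W switchers.

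On rescue, Protocol 5.1 says of RHBX entrants: "Patients who were rescued to ixekizumab 80 mg Q2W will remain on ixekizumab 80 mg Q2W in open-label fashion". In Table RHBY.2, Q2W is the only rescue regimen shown, and only for RHBX. On blinding, Protocol 7.3 says that patients, site personnel and study team "will remain blinded to the initial treatment assigned in the originating study (RHBV, RHBW, or RHBX) until the time of datalock", which for RHBX is the Week 52 datalock.

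**The concern.** Rescue happens after randomization and is likely to be related to response. When rescue is to Q2W, a rule framed by regimen acts on it in one dose only. A rescued Q4W patient has changed regimen and leaves the population. A rescued Q2W patient has not changed regimen and remains.

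The SAP reports the two doses side by side from Week 0 of the originating study to Weeks 64 and 104. It also uses this population for Week 64 subgroup summaries, including one by originating study (SAP 6.14.1). If rescued patients do worse than others, part of any apparent advantage of Q4W over Q2W would come from the selection rule and not from the drug.

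**Working it through.** The documents state no figure on this point, so there is none to reproduce. The check follows one patient of each kind through the definitions and then illustrates the direction of the effect.

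**Text check**

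1. A patient randomized to Q4W and moved to open-label Q2W in the originating study fails the same-regimen clause of SAP 6.1.1 and is also named as excluded. Out.
2. A patient randomized to Q2W and rescued to open-label Q2W passes the same-regimen clause, meets the Q2W footnote and matches no named exclusion. In, provided the other conditions are met.
3. Under Protocol 10.2, neither patient is excluded for the switch or rescue.
4. A patient escalated from Q4W to Q2W after Week 64 is not removed from the population. SAP 6.1.2.2 uses only the data on Q4W, and refers to modified nonresponder imputation for categorical endpoints and modified baseline observation carried forward for continuous ones.

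**Whether Q2W patients were rescued at all.** Neither document says so. The inference is that RHBX assignment was blinded to Week 52 datalock, so rescue could not readily be confined to one arm.

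**Direction and possible size (all inputs assumed).** Take equally effective doses and the same rescued share *s* in each arm. Let *rn* be the response in patients not rescued and *rr* the response in rescued patients.

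- Q4W shown = *rn*
- Q2W shown = (1 − *s*) × *rn* + *s* × *rr*
- Gap = *s* × (*rn* − *rr*)

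With *rn* = 60%, the gap in percentage points in favour of Q4W is:

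| *rr* | *s* = 5% | 10% | 20% | 30% |
|---|---|---|---|---|
| 60% | 0 | 0 | 0 | 0 |
| 40% | 1 | 2 | 4 | 6 |
| 20% | 2 | 4 | 8 | 12 |
| 10% | 2.5 | 5 | 10 | 15 |

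Only RHBX is shown to have had rescue, so in the pooled population *s* is the RHBX share times the RHBX rescue rate. If RHBX supplies one third of each arm and 20% to 40% of its patients were rescued, *s* = 1/3 × 20% = 6.7% to 1/3 × 40% = 13.3%. At *rr* = 20% the gap is 6.7% × 40 = 2.7 points to 13.3% × 40 = 5.3 points. In the RHBX-only subgroup there is no dilution: 20% × 40 = 8 points to 40% × 40 = 16 points.

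**Under a common rule.** If rescue counts as nonresponse in both doses, each column shows (1 − *s*) × *rn*. If rescued patients are dropped from both, each shows *rn*. Either way the artificial gap is 0 when the doses are equally effective and equally often rescued.

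**The case against.** The strongest defence is that this is openly an on-regimen population. The definition and footnotes say that each column contains patients who stayed on that regimen, and it is not offered as an intention-to-treat comparison of doses. The summary belongs to the other secondary objectives, has no inferential statistics, and feeds no primary, major secondary or multiplicity-controlled result. All of this stands, and it limits the consequence. It does not answer the point that an on-regimen rule removes rescue in one column and not in the other.

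A reader might infer that the Q4W column has been cleared of its failures while the Q2W column has not. The documents do not support that. Poor responders who stayed on Q4W remain, and patients retreated in Period 2 leave both columns.

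A reader might also infer a clear contradiction with the handling of escalation after Week 64. The contrast is only partial. SAP 6.1.2.2 gives observed cases as a categorical summary, so later escalators drop out of that denominator. The modified nonresponder rule in SAP 6.3.2 lists flare retreatment and discontinuation for an adverse event or lack of efficacy. It does not list escalation or rescue.

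Finally, the documents give neither the RHBX rescue rules nor the rescue counts, and rescue of Q2W patients is inferred.

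**Conclusion.** The point holds as a difference in selection between two descriptive columns. Read literally, SAP 6.1.1 and the table footnotes exclude rescued Q4W patients and keep rescued Q2W patients, and this narrows the protocol's definition. Q4W reads too high relative to Q2W if two conditions are met: some Q2W patients were rescued in RHBX, and rescued patients respond less well. If they respond equally, there is no distortion.

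The size cannot be computed from the documents. The figures above show how it scales and are not estimates, and dilution across the three studies pushes the pooled effect toward the low end. It would be wrong to conclude that the Q4W rate is overstated by a known amount, or that any tested dose comparison is affected. This is a cheap improvement to a descriptive analysis.

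**What to change.** Apply one rule to originating-study rescue in both doses.

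- **Preferred.** Keep all patients randomized to each dose who otherwise qualify. From the date of rescue or switch, count them as nonresponders for categorical endpoints and carry forward the last pre-rescue value for continuous endpoints. State this explicitly, because SAP 6.3.2 does not cover rescue or escalation. It must apply to both doses: counting rescue as failure in Q4W only would reverse the asymmetry.
- **Wording.** Amend the same-regimen clause in SAP 6.1.1 as well as the named exclusion, since deleting the exclusion alone would leave switchers out. Bring the footnotes to Tables RHBY.6.1, RHBY.6.5 and RHBY.6.7 into line, and explain the departure from Protocol 10.2.
- **Alternative.** If the on-regimen population stays as the main summary, exclude rescued patients from both doses, report the numbers rescued or switched by randomized dose, and add the common-rule summary as a sensitivity analysis.

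The cost is some SAP wording and one extra derivation. The analysis already runs from Week 0 of the originating studies, so the data should be in hand. The long-term figures become slightly less favourable. Under the pooled assumptions above, a 60% column would read 60% × (1 − 6.7%) = 56.0% to 60% × (1 − 13.3%) = 52.0%.

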## 5.2. Determination of Sample Size

It is estimated that approximately 750 patients will enter the long-term extension study (RHBY) after completion of Studies RHBV, RHBW, or RHBX. This sample size is estimated based on the 1-year retention rates from ixekizumab psoriasis studies and from 1 secukinumab radiographic (rad)-axSpA study (Baeten et al. 2015), which had a retention rate of approximately 85%. It is anticipated that approximately 30% of the 750 patients will meet the entry criteria for randomized-withdrawal (Sieper et al. 2015). Approximately 100 patients who achieved a state of sustained remission on IXE80Q4W will be randomized in a 2:1 ratio to IXE80Q4W or placebo, and approximately 100 patients who achieved a state of sustained remission on IXE80Q2W will be randomized in a 2:1 ratio to IXE80Q2W or placebo in the double-blind RWR period. This total sample size of 200 will provide over 99% power to detect a difference in the proportion of patients who do not experience a flare between the Combined Ixekizumab treatment group (including Q2W and Q4W) and placebo using a 2-sided Fisher's exact test at the 0.05 level, assuming the flare rates are 10% for ixekizumab and 70% for placebo. Sample size and power calculations are calculated using nQuery+nTerim 3.0.

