## 5.3. Method of Assignment to Treatment

During the Lead-In Period (Period 1), patients who are previously receiving ixekizumab treatment during Studies RHBV and RHBW will, as of Week 0 in Study RHBY, continue to receive the same ixekizumab treatment regimen they are on at the end of the originating study, but now in open-label fashion.

For patients who are previously in Study RHBX, treatment during the Lead-In Period will be assigned as follows:

- patients who are rescued to open-label IXE80Q2W will remain on IXE80Q2W in open-label fashion.
- patients who are receiving blinded treatment with either IXE80Q2W or IXE80Q4W will continue on their ixekizumab dose regimen in blinded fashion.
- patients who are receiving blinded treatment with placebo will be assigned to receive blinded treatment with IXE80Q4W.

During the Extension Period, including RWR (Period 2), patients in Group A who do not meet entry criteria for RWR will continue to receive the same ixekizumab dose regimen that they are receiving during the Lead-In Period (IXE80Q2W or IXE80Q4W).

During the Extension Period, patients in Group B who have achieved a state of sustained remission, and meet the criteria for randomized withdrawal (RW) (see Section 5.1), will be assigned to treatment groups as follows by a computer-generated random sequence using an interactive web-response system (IWRS).

- Patients in the IXE80Q2W treatment group will be re-randomized to either IXE80Q2W or placebo at 2:1 ratio allocation and will be stratified by region and originating study.

- Patients in the IXE80Q4W treatment group will be re-randomized to either IXE80Q4W or placebo at 2:1 ratio allocation and will be stratified by region and originating study.

The IWRS will be used to assign double-blind investigational product to each patient. Site personnel will confirm that they have located the correct investigational product package by entering a confirmation number found on the package into the IWRS.

During the Long-Term Extension Period (Period 3), patients will continue the same treatment that they are receiving at the end of Period 2.

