#### **6.1.4. General Consideration for Analyses at Week 56 for the 2-year Radiographic Progression in Spine**

Assessment of 2-year radiographic progression in the spine from baseline in studies RHBV and RHBW to Week 56 (Group A: Visit 9/Group B: Visit 513) in RHBY will be evaluated for the Ixekizumab Structure Population (Ixe-Structure) as defined in Section 6.1.1.

Descriptive statistics will be provided for the 2-year radiographic progression in spine measured by change in modified Stoke Ankylosing Spondylitis Spinal Score (mSASSS), the proportion of non-progressors measured by change in Total mSASSS <2 and mSASSS <=0, respectively, and proportion of patients with no new syndesmophyte will be summarized as well.

Cumulative Probability Plot for change from baseline in mSASSS at year 2 will be provided for each ixekizumab treatment group.

Analysis will be done for Ixekizumab Structure Population who have been treated with ixekizumab for at least 24 months, namely who were initially assigned ixekizumab 80 mg Q4W or Q2W in originating studies and not re-randomized to placebo at Week 24 in RHBY. Data will also be summarized for all patients available.

Additional analysis will be repeated for Ixekizumab Structure Population, and Ixekizumab Structure Population who did not participated in the RW period.

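### The long-term efficacy population loses about one third of the sustained-remission patients through re-randomisation to placebo, with no reweighting, so this group is under-represented

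*SAP*

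**What the plan says.** A stated objective in both documents is the long-term effect of each ixekizumab regimen through Week 104. Protocol 10.2 answers it in patients randomised to ixekizumab "at Week 0 of the originating studies and consistently received ixekizumab in RHBY". SAP 6.1.1 narrows this to patients on the same regimen through Week 64. It lists as excluded "patients who were randomized to placebo during Period 2 of RHBY", patients retreated in Period 2, and patients switched from Q4W to open-label Q2W in the originating study.

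The placebo exclusion can only touch Group B, because only patients meeting the ASDAS remission rule at Weeks 16 and 20 are re-randomised. SAP 5.3 gives the allocation: "Patients in the IXE80Q4W treatment group will be re-randomized to either IXE80Q4W or placebo at 2:1 ratio allocation". The Q2W arm has the same ratio. Everyone else (Group A) continues ixekizumab.

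SAP 6.1.2.2 summarises this population at every scheduled visit from Week 0 of the originating study. The methods listed there and in Table RHBY.6.5 are observed cases, mBOCF, mNRI and MMRM. None uses weights, and none brings back a patient who is outside the population. Table RHBY.6.1 marks the analysis as descriptive.

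**The concern.** The re-randomisation was built for the withdrawal question. Here it changes the patient mix used for a different question. Group B is defined by ASDAS, and the long-term endpoints include ASDAS <1.3 and ASDAS <2.1, so the mix is altered on a close correlate of the outcome.

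The loss is hardest to justify up to RHBY Week 24. Until then the patients later assigned to placebo were on uninterrupted ixekizumab, yet all their data go because of a later random allocation. The SAP handles similar cases differently. The Lead-In Period Safety Population keeps these patients and drops only their time on placebo. Patients escalated from Q4W to Q2W after Week 64 keep their Q4W data (6.1.2.2).

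With no test planned, the point estimate is the result for this objective.

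**Working it through.** **Inputs from the documents.**
- Allocation (SAP 5.2): "will be randomized in a 2:1 ratio to IXE80Q4W or placebo", and likewise for Q2W.
- Group B share: "It is anticipated that approximately 30% of the 750 patients will meet the entry criteria for randomized-withdrawal". SAP 5.2 then plans on about 200 randomised, and 200/750 = 26.7%. Protocol 10.1 also considers 20%.
- Period 2 flare: "assuming the flare rates are 10% for ixekizumab and 70% for placebo".

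**The plan's own figure.** The documents give no figure for long-term response. The nearest is the stated power of over 99% with 200 patients (2-sided Fisher's "exact test at the 0.05 level"). Exact enumeration with 133 against 67 gives more than 0.9999, so that figure stands. It does not bear on this point.

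**Notation.** p = Group B share of RHBY entrants; f = flare rate on continued ixekizumab; q = response in unflared Group B; a = response in Group A. The values of q and a are assumptions.

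**Step 1. Placebo exclusion alone.** Retained Group B share s1 = (2p/3)/(1 − p/3).
- p = 30%: 0.200/0.900 = 22.2%
- p = 26.7%: 0.178/0.911 = 19.5%
- p = 20%: 0.133/0.933 = 14.3%

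Shift in reported response = (s1 − p) × (Group B response − Group A response). At p = 30% the factor is 0.222 − 0.300 = −0.078. A gap of 10 points gives −0.8, 30 points gives −2.3 and 50 points gives −3.9.

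**Step 2. Add the retreatment exclusion.** Only Group B is retreated on flare, so on the ixekizumab arm this removes the patients who flared. The share becomes s2 = (2p/3)(1 − f)/[(1 − p) + (2p/3)(1 − f)]. At p = 30% and f = 10%, s2 = 0.18/0.88 = 20.5%.

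Up to Week 24 the later flarers had recently met the remission rule, so their loss also lowers the Group B share. Both exclusions then plausibly act in the same direction, low.

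**Step 3. Week 64, flarers counted as nonresponders in the target.** Bias = [s2·q + (1 − s2)·a] − [p(1 − f)q + (1 − p)a].

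| Assumed q, a (p = 30%, f = 10%) | SAP population | Target | Bias (points) |
|---|---|---|---|
| ASDAS <1.3: 75%, 10% | 23.3% | 27.3% | −4.0 |
| 95%, 20% | 35.3% | 39.7% | −4.3 |
| 95%, 50% | 59.2% | 60.7% | −1.4 |
| 95%, 70% | 75.1% | 74.7% | +0.5 |
| 95%, 80% | 83.1% | 81.7% | +1.4 |

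The bias is zero at a/q = [p(1 − f) − s2]/(p − s2) = 0.0655/0.0955 = 0.69. The break-even is 0.83 at f = 5% and 0.47 at f = 20%. With f = 20%, q = 95% and a = 50%, the bias is already +0.6.

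**Step 4. What a weight of 1.5 does.** With q = 95%, a = 50% and f = 10%:
- Weighting with retreated patients still excluded: (0.27 × 0.95 + 0.70 × 0.50)/0.97 = 62.5%, against a target of 60.7% (+1.9). For a from 20% to 80% the overshoot is +1.2 to +2.5.
- Weighting with retreated patients kept as nonresponders: 0.27 × 0.95 + 0.70 × 0.50 = 60.7%, the target.

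**Step 5. Cost of the weights.** Kish design effect at p = 30%: 0.90 × (0.70 × 1² + 0.20 × 1.5²)/(0.70 + 0.20 × 1.5)² = 0.90 × 1.15 = 1.035.

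**The case against.** A reader might infer that long-term response is biased low at every visit. The documents do not support that. The same SAP sentence removes the ixekizumab-arm patients who flared, and Step 3 shows that the Week 64 sign can then go either way. At Week 0 there is no response to bias. Direction also depends on the target. Compare instead with everyone randomised to ixekizumab in the originating studies, and count an assumed 15% not retained as nonresponders. With q = 95%, f = 10% and a from 20% to 80%, the Week 64 bias is then +1.6 to +13.7 points. If those 15% respond at 20%, it is −1.4 to +10.7.

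A second tempting reading is that the known 2:1 ratio makes a 1.5 weight an exact correction. Step 4 shows that weighting alone overshoots.

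A third is that the 24-month structure analysis in SAP 6.1.4, limited to patients "not re-randomized to placebo at Week 24 in RHBY", has the same defect. That section also plans summaries for all available patients and for the full Ixekizumab Structure Population, and 6.14.1 adds a Group A or B subgroup there. The structure analysis needs no change on this account.

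It is also fair to say that the analysis is descriptive and an other secondary objective, and that the population is openly defined as consistently treated patients. Group A/B status is a listed baseline characteristic, and Group B response in Period 2 is reported in the RW ITT Population. This limits the importance of the point. It does not let a reader repair the table, because 6.14.1 plans no Group A/B split of long-term response. The RW ITT Population also includes patients first randomised to placebo or adalimumab.

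Finally, the 30% refers to all 750 entrants, including those same patients, so it only approximates the share in this population.

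**Conclusion.** The concern holds in a limited form. The exclusion, the one third and the absence of weighting are all in the documents. Among RHBY entrants, Group B falls from 30% to 22.2% of those retained (26.7% to 19.5%; 20% to 14.3%). Taken alone at 30%, this costs about 1 to 4 points of response for gaps of 10 to 50 points. Low is the plausible direction for post-baseline visits up to RHBY Week 24.

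At Week 64 the net sign is not settled. It stays low for ASDAS <1.3 under a large gap between the groups. It can reverse once Group A response exceeds about 0.69 of unflared Group B response at the plan's 10% flare rate, and sooner if flares are more common.

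The 2:1 ratio, the group shares and the 10% come from the documents. Every response rate and gap is assumed. This is a worthwhile low-cost improvement to a descriptive table. It does not affect the primary or major secondary tests.

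**What to change.** In SAP 6.1.1 and 6.1.2.2, state the target population: patients first randomised to ixekizumab who entered RHBY and stayed on that regimen until Week 24. Keep the planned unweighted tables and add a supportive version of the response-rate and mean-change tables, built as follows.

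1. **Visits up to RHBY Week 24.** Include all Group B patients' own on-ixekizumab data, unweighted, both those later randomised to placebo and those later retreated.
2. **Visits after Week 24.** Weight ixekizumab-arm Group B patients by 1.5 (the inverse of 2/3) and Group A by 1. Keep ixekizumab-arm patients retreated in Period 2. Count them as nonresponders for categorical endpoints (mNRI, 6.3.2) and carry forward their last value before retreatment for continuous endpoints (6.3.3). Both rules are already in the SAP, and the protocol's definition of this population does not name retreated patients as an exclusion.

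The two parts of step 2 must go together, because weighting without the retreated patients overshoots.

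The cost is some SAP wording, one extra set of descriptive summaries and about 3% to 4% of effective sample size (design effect 1.027 at 20% Group B, 1.035 at 30%, 1.040 at 40%). The number of contributing patients changes after Week 24, so the table should show it at each visit.
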